12.3 Significance level and power of the clinical trial

The statistical significance level takes the one-tailed significance level of $\alpha=0.025$, 80% power (1- β).

12.4 Expected drop-out rate

Expected drop-out rate is not more than 20%.

Confidential and Proprietary

This document contains confidential and proprietary information on Smith & Nephew PLC and Smith & Nephew, Inc. and is only available to Smith & Nephew and its manufacturers. Without prior written approval of Smith & Nephew, the content cannot be replicated, printed totally/partially or disclosed in any other way, and anyone must use it as per the requirements, either expressed or implied by Smith & Nephew.

Study Protocol - Device	Smith+Nephew
A Prospective, Multi-center, Randomized Clinical Study to Evaluate the Safety and Effectiveness of Biosure Regenesorb Interference Screw in Arthroscopic Reconstruction of Cruciate Ligaments in Chinese Patients	Study No.: BIOSURE RG.SMD.PMA.2019.01
	Version: V2.0/July 3rd, 2020
	Page 48 of 74

12.5 Criteria for acceptability/unacceptability of clinical trial result

Primary efficacy endpoint (the Lysholm score at 12 months after operation): If the lower limit of 95% CI for the efficacy difference between two groups is greater than the non-inferiority margin, it is considered that the investigational product is non-inferior to the control product, the statistical hypothesis is valid and the result of clinical trial is qualified; otherwise, the hypothesis is invalid, and the result of clinical trial is unacceptable.

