12.1.3 Primary efficacy endpoints

Primary efficacy evaluation will be based on Full Analysis Set (FAS) and Per-Protocol Set (PPS). For the statistical description and inference of the data, the applicable descriptive endpoints and hypothesis testing methods will be selected based on the characteristics of the data.

The primary efficacy endpoint of this study is Lysholm score at 12 months after operation. The non-inferiority testing is performed for efficiency of primary efficacy endpoint, and the test hypothesis is as follows:

Invalid hypothesis: $H_0: \mu_1 - \mu_2 \leq -\delta$

Alternative hypothesis: $H_1: \mu_1 - \mu_2 > -\delta$,

where, μ_1 and μ_2 are the Lysholm scores in the investigational group and control group, respectively. δ is a non-inferiority critical value. At $\alpha=0.025$ (one-sided test), the hypothesis test is carried out using a two-sided t-test. A non-inferiority test is carried out on the Lysholm scores in the investigational group and control group. The 95% confidence interval between the two groups is calculated.

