12.2 Calculation of sample size

12.2.1 Total Sample Size

The primary efficacy endpoint of this study is the Lysholm score at 12 months after operation; the trial is designed as a non-inferiority trial. According to references, the non-inferiority margin is set as 5 in this study. Assuming that the variance in both the investigational group and control group is 9, the difference between two groups is 0, the significance level is set to $\alpha=0.025$ (one-tailed), power $1-\beta=0.80$, the calculation formula of sample size is analyzed by referring to the non-inferiority of quantitative indicator:

Confidential and Proprietary

This document contains confidential and proprietary information on Smith & Nephew PLC and Smith & Nephew, Inc. and is only available to Smith & Nephew and its manufacturers. Without prior written approval of Smith & Nephew, the content cannot be replicated, printed totally/partially or disclosed in any other way, and anyone must use it as per the requirements, either expressed or implied by Smith & Nephew.

Study Protocol - Device	Smith+Nephew
A Prospective, Multi-center, Randomized Clinical Study to Evaluate the Safety and Effectiveness of Biosure Regenesorb Interference Screw in Arthroscopic Reconstruction of Cruciate Ligaments in Chinese Patients	Study No.: BIOSURE RG.SMD.PMA.2019.01
	Version: V2.0/July 3rd, 2020
	Page 47 of 74

$$n_T = n_C = \frac{2(Z_{1-\alpha/2} + Z_{1-\beta})^2 \sigma^2}{(D - \Delta)^2}$$

In which, σ is the standard deviation; D is the mean difference between two groups, which is expected to be detected, $D=uT-uC$; Δ is the non-inferiority margin. At least 51 subjects should be included in each group in order to achieve 80% power, 102 in total. In consideration of 20% drop-out rate, 64 subjects are planned to be included in each group, 128 subjects in total; 12 subjects are planned to be added to increase the success rate of trial, 140 subjects in total and 70 in each group.

The estimation of sample size is completed by using PASS13.

12.2.2 Number of Subjects with Each Disease in Clinical Trial and Reason for Determination

In this trial protocol, it is strictly required that patients should be enrolled in compliance with the inclusion/exclusion criteria. It can be considered that all the patients have the same type of disease, and are not further divided.

12.2.3 In multi-center clinical trial, minimum and maximum number of subjects in each clinical trial institution and justification

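### The pass/fail rule in section 12.5 lacks the minus sign: with the plan's margin of 5 it reads as a lower limit above +5, but the design fits only -5

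*Combined protocol and SAP*

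**What the plan says.** Three sections of the combined protocol and SAP bear on the decision threshold.

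- **Section 12.5** gives the acceptance criterion: "If the lower limit of 95% CI for the efficacy difference between two groups is greater than the non-inferiority margin", the product is declared non-inferior. The alternative is stated just as firmly: "otherwise, the hypothesis is invalid, and the result of clinical trial is unacceptable". The section prints no number, no sign and no direction of subtraction.
- **Section 12.2.1** gives the only number: "According to references, the non-inferiority margin is set as 5 in this study". It carries no sign. The same section defines D as the investigational mean minus the control mean, assumes a true difference of 0, and uses Δ for the margin in the sample-size formula.
- **Section 12.1.3** sets out the hypotheses for investigational minus control. The null is a difference at or below -δ and the alternative is a difference above -δ. On the symbol itself it says only that "δ is a non-inferiority critical value". It gives δ no value.

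Nowhere does the plan print -5.

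**The concern.** Putting the plan's own number into its own acceptance sentence gives a lower confidence limit above 5. On a 0-100 scale where higher is better (section 10.1.5.1), that requires the new screw to be shown more than 5 points better than the control. The alternative hypothesis in section 12.1.3 asks only that it be not more than δ points worse. The decision sentence and the hypothesis it is meant to decide therefore do not agree.

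Section 12.5 is the formal criterion on which the registration result is accepted or rejected. Applied literally, it would fail a device that is exactly as good as the control, almost without exception.

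**Working it through.** **Inputs.** Margin 5, true difference 0, one-sided α 0.025 and power 80% (section 12.2.1); 1:1 allocation (10.1.3.3); two-sided 95% CI (12.1.1, 12.1.3, 12.5); 70 randomized per arm with up to 20% drop-out, so 70 × 0.8 = 56 evaluable (12.2.1, 12.4).

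**Assumption on spread.** Section 12.2.1 prints a variance of 9. I use SD 9, because that value reproduces the plan's sample size. SD 3 is shown at the end.

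**Step 1: reproduce the plan's figure.** The plan says "At least 51 subjects should be included in each group in order to achieve 80% power". The formula gives

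n = 2(1.960 + 0.8416)² × 9² / (D − Δ)² = 2 × 7.849 × 81 / 25 = 50.9, rounded up to 51 per group.

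The plan's number reproduces. With D = 0, however, (D − Δ)² is 25 whether Δ is +5 or −5, so the formula alone cannot settle the sign.

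**Step 2: find what does settle the sign.** Three things fit only -5:

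1. The hypotheses in 12.1.3, where the boundary is -δ with a positive δ.
2. The conclusion drawn in 12.5 itself, which is non-inferiority.
3. The claim of 80% power at a true difference of 0. A rule requiring the lower limit to exceed +5 cannot have that power (step 3).

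**Step 3: probability that a truly equal device passes.** SE = 9√(2/n) with n per arm. The rule passes when the observed difference minus t(0.975, 2n−2) × SE exceeds the threshold. The probability comes from the noncentral t distribution with 2n−2 degrees of freedom and noncentrality (0 − threshold)/SE.

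| Evaluable per arm | SE | Pass probability, threshold -5 | Pass probability, threshold +5 |
|---|---|---|---|
| 51 | 1.782 | 79.3% | 1.1 × 10⁻⁶ |
| 56 | 1.701 | 83.0% | 5.5 × 10⁻⁷ |
| 70 | 1.521 | 90.4% | 8.8 × 10⁻⁸ |

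The 79.3% at 51 per arm is the t-based counterpart of the plan's 80%; the normal approximation gives 80.1%.

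**Step 4: observed difference needed at 56 per arm.** If the observed SD is 9, the CI half-width is 1.982 × 1.701 = 3.37.

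- Threshold -5: the observed difference must exceed -5 + 3.37 = -1.63.
- Threshold +5: it must exceed 5 + 3.37 = +8.37.

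Under the literal wording, 80% power at 56 per arm would need a true advantage of about 5 + (1.960 + 0.8416) × 1.701 = 9.77 points, whereas the plan assumes 0.

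**Step 5: sensitivity to the SD.** If the printed variance of 9 is taken literally (SD 3), the formula gives 2 × 7.849 × 9 / 25 = 5.65, so 6 per arm, which does not match 51. At 56 per arm with SD 3 the two pass probabilities are above 99.99% and below 10⁻²⁰. The contrast between the two readings remains.

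**The case against.** The strongest reply is that the plan corrects itself. Section 12.5 prints no number; +5 appears only when it is joined to 12.2.1 and the signed hypotheses in 12.1.3 are passed over. The same sentence in 12.5 refers to non-inferiority and to the statistical hypothesis, and the only such hypothesis carries -δ. A trained reader would use -5. On this view the pass probabilities of the order of 10⁻⁶ to 10⁻⁸ describe a reading nobody would adopt.

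Much of that stands. The threshold can be recovered, the practical risk is low, and the small probabilities show how far apart the readings are; they do not measure expected harm. The contradiction still remains, because a formal acceptance criterion should not need two other sections to supply its sign. Nor is a later correction the natural remedy: section 12.7 has the statistical analysis plan developed before the trial but issued after database lock.

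A second reply is that the fault lies in 12.2.1. If the margin were defined as a signed boundary of -5, the wording of 12.5 would be right. That is a fair point about where to put the correction. But 12.2.1 prints 5, and 12.1.3 uses a positive δ with an explicit minus, so the plan has not adopted the signed convention. Either way, the sign has to be written down.

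A third reply is that the corrected sentence would still not say whether FAS, PPS or both must meet the criterion. That is true, but it is a separate matter.

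**Conclusion.** The concern holds. The acceptance rule, read with the only value the plan gives for its margin, contradicts the alternative hypothesis. The defect is one omitted sign in the decision sentence, together with a δ that is never given a value. The design and the sample size are unaffected: 51 per group reproduces.

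The size of the discrepancy is 10 points on the threshold. For a truly equal device it separates a likely pass from a near-certain failure. The quoted probabilities rest on SD 9, a true difference of 0 and a two-sample t interval; the conclusion does not depend on the choice between SD 9 and SD 3. Because the intended rule can be inferred, this should be fixed but does not undermine the trial.

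**What to change.** - **Section 12.5:** replace the condition with wording such as: *If the lower limit of the two-sided 95% CI for the difference in mean 12-month Lysholm score (investigational minus control) is greater than -5, the investigational product is non-inferior to the control product.*
- **Section 12.2.1:** define the sign once: δ = 5, decision threshold -δ = -5, and Δ = -5 in the formula.
- **Section 12.1.3:** state δ = 5. Optionally, describe the test as a one-sided 0.025 test of a difference at or below -5, equivalent to the interval in 12.5.

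The cost is wording in the protocol and SAP, plus the ethics committee approval that section 15.1 requires for a protocol amendment. Patients, data collection, analysis and sample size do not change.

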12.6 Criteria and reason for terminating the trial based on the statistical consideration

This trial does not include interim analysis and does not terminate the trial according to statistical reasons.

12.7 Statistical Method of All Data, Together with the Handling Method of Missing, Unused and Wrong Data (Including Discontinuation and Withdrawal) and Unreasonable Data

The statistical analysis plan is developed before the trial. The statistical analysis programming and logic test programming are conducted according to the statistical analysis plan after database locking, then the simulation database test is conducted and the statistical analysis plan is issued according to the results.

The Last Observation Carried Forward (LOCF) is used for imputation for missing data of primary efficacy endpoint. The handling of the outliers is to inquire the investigator about the unreasonable data and determine how to resolve the queries which are given by the data manager.

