10.1.5.2 Secondary efficacy endpoints

- Lysholm Score (Month 6, Month 24)
- International Knee Documentation Committee (IKDC) score (at months 6, 12 and 24)

The scoring scale was proposed in 2000 after being repeatedly revised by major sports medicine and medical organizations in Europe and America. The scale is composed of a knee evaluation form (10 items) and a knee ligament examination form (8 items), involving joint pain, sport level and ability of daily activities. The total score is 0-100. The IKDC scale is for evaluating the symptoms, functions and physical activities of the knee joint, helping compare different knee diseases.

- Drawer Test (Month 6, Month 12, Month 24)

Anterior drawer test: It is used for ACL examination. The patient should be supine with the knees flexed to 90 degrees and the feet flat on table and keep relaxed. The examiner sits on the examination table against the patient feet for fixation, grasps the tibia of the knee and draws the shank forward. The patient will be diagnosed with forward straight instability if the tibia is forward displaced 5 mm more than the uninjured side.

Posterior drawer test: It is used for PCL examination. The patient should be supine with the knees flexed to 90 degrees. The examiner places both hands behind the knee joint, with the thumbs on the extensor aspect. The proximal end of shank is repeatedly drawn backward. The posterior displacement of the tibia along the femur suggests partial or complete CL rupture.

Confidential and Proprietary

This document contains confidential and proprietary information on Smith & Nephew PLC and Smith & Nephew, Inc. and is only available to Smith & Nephew and its manufacturers. Without prior written approval of Smith & Nephew, the content cannot be replicated, printed totally/partially or disclosed in any other way, and anyone must use it as per the requirements, either expressed or implied by Smith & Nephew.

Study Protocol - Device	Smith+Nephew
A Prospective, Multi-center, Randomized Clinical Study to Evaluate the Safety and Effectiveness of Biosure Regenesorb Interference Screw in Arthroscopic Reconstruction of Cruciate Ligaments in Chinese Patients	Study No.: BIOSURE RG.SMD.PMA.2019.01
	Version: V2.0/July 3rd, 2020
	Page 32 of 74

- Lachman Test (Month 6, Month 12, Month 24)

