10.2.2.2 Pre-operative study activities

Prior to the operation, the following information must be collected:

Confidential and Proprietary

This document contains confidential and proprietary information on Smith & Nephew PLC and Smith & Nephew, Inc. and is only available to Smith & Nephew and its manufacturers. Without prior written approval of Smith & Nephew, the content cannot be replicated, printed totally/partially or disclosed in any other way, and anyone must use it as per the requirements, either expressed or implied by Smith & Nephew.

Study Protocol - Device	Smith+Nephew
A Prospective, Multi-center, Randomized Clinical Study to Evaluate the Safety and Effectiveness of Biosure Regenesorb Interference Screw in Arthroscopic Reconstruction of Cruciate Ligaments in Chinese Patients	Study No.: BIOSURE RG.SMD.PMA.2019.01
	Version: V2.0/July 3rd, 2020
	Page 35 of 74

- Demographics include:
 - Age at surgery (calculated from date of birth)
 - Gender (male/female)
 - Occupation
 - Height (in cm) and body weight (in kg)
 - Body mass index (BMI)
- Vital signs: pulse, blood pressure, respiration and body temperature
- Physical examination status
- Medical history will be obtained and will include:
 - Previous medical history (HEENT, respiratory, gastrointestinal, hematological, cardiovascular, endocrine/metabolic, musculoskeletal, immunological, neurological, genitourinary, prior surgery, others)
 - Tobacco use and alcohol intake (tobacco use: never used, past use, current use; alcohol intake)
 - Closure of epiphyseal plate
 - Current medical history of knee diseases: time of knee injury, cause of knee injury, conditions of the studied knee side (left/right) and the contralateral knee joint, cause of CL rupture or tear, other combined knee injury, knee degeneration and whether or not to totally excise the medial or lateral meniscus
 - Previous surgeries on the affected knee joint (For surgery history, fracture fixation, arthroscopy, ligament surgery, autologous cell transplantation or other surgery, please specify)
 - Safety events
 - All combination drugs associated with AEs or SAEs are recorded.

In addition, subjects will be evaluated clinically pre-operatively using:

- Lysholm Score
- IKDC Score
- Drawer test

Confidential and Proprietary

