12.9 Selection criteria and justification of subjects included in the analysis

12.9.1 Full Analysis Set (FAS)

Confidential and Proprietary

This document contains confidential and proprietary information on Smith & Nephew PLC and Smith & Nephew, Inc. and is only available to Smith & Nephew and its manufacturers. Without prior written approval of Smith & Nephew, the content cannot be replicated, printed totally/partially or disclosed in any other way, and anyone must use it as per the requirements, either expressed or implied by Smith & Nephew.

Study Protocol - Device	Smith+Nephew
A Prospective, Multi-center, Randomized Clinical Study to Evaluate the Safety and Effectiveness of Biosure Regenesorb Interference Screw in Arthroscopic Reconstruction of Cruciate Ligaments in Chinese Patients	Study No.: BIOSURE RG.SMD.PMA.2019.01
	Version: V2.0/July 3rd, 2020
	Page 49 of 74

Full Analysis Set (FAS): According to the basic principle of Intention To Treat (ITT), all subjects who are randomized in the trial and have at least one effectiveness evaluation are included in the Full Analysis Set. The Last Observation Carried Forward (LOCF) is used for analysis when the primary efficacy endpoint is missing.

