12.9.2 Per-protocol Set (PPS)

Per Protocol Set (PPS): it refers to a set of subjects that complete the trial, excluding those with serious protocol violation.

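### LOCF is the only stated method for a missing 12-month Lysholm score, no missing-data sensitivity analysis is given, and the joint role of FAS and PPS is left open

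*Combined protocol and SAP*

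**What the plan says.** Section 12.7: "The Last Observation Carried Forward (LOCF) is used for imputation for missing data of primary efficacy endpoint". Section 12.9.1 repeats the rule inside the FAS definition and sets membership as follows: "all subjects who are randomized in the trial and have at least one effectiveness evaluation are included in the Full Analysis Set". It does not say that the evaluation must be post-operative. The PPS in 12.9.2 is limited to completers: "it refers to a set of subjects that complete the trial, excluding those with serious protocol violation".

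The follow-up schedule and sections 10.1.5.2 and 10.2.2.2 place the Lysholm score before operation and at months 6, 12 and 24. The only scores available to carry to month 12 are therefore the pre-operative and month-6 ones. Section 10.1.4.7 justifies 12 months of follow-up partly by functional recovery.

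Section 12.1.3 bases the primary evaluation on both FAS and PPS. The success rule in 12.5 rests on one interval and names no set: "If the lower limit of 95% CI for the efficacy difference between two groups is greater than the non-inferiority margin". The limit is read here as -5, from the margin of 5 in 12.2.1 and the hypotheses in 12.1.3.

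Section 10.1.4.4 asks subjects who stop early to try to complete the final evaluation, but also says that follow-up need not continue after withdrawal. Section 12.4 puts drop-out at no more than 20%. Section 12.1.2 plans a comparison of total dropout and a list of reasons for non-completion. Section 12.7 refers to a statistical analysis plan that is not among the supplied documents.

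**The concern.** A carried score comes from an earlier stage of recovery. In the FAS it pulls the estimated difference towards whatever the difference was at month 6, and it shifts the estimate if the arms lose different numbers of subjects. The PPS avoids carried values because it keeps completers, but it protects the conclusion only if loss is unrelated to outcome and both sets must pass. The text does not require the second.

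Outcome-related loss is the harder case. A subject whose knee fails after month 6 and who then leaves is scored by LOCF at the pre-failure value and is dropped from the PPS, so the two sets err together. Section 13.2 itself links loss in earlier studies to limited functional recovery, though in older patients and early follow-up. Section 10.1.4.4 also lets investigators withdraw a subject for a serious adverse event.

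At stake is a registration decision taken on one confidence limit against 5 points, with choices that could still be made after the data are seen.

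**Working it through.** **Plan's own figures.** Margin 5, true difference 0, one-sided alpha 0.025, power 80% (12.2.1). The formula is n = 2(z0.975 + z0.80)²σ²/5². With σ = 9, n = 2 × (1.960 + 0.842)² × 81/25 = 50.9, so 51 per group; 51/0.80 = 63.75, so 64. Both figures reproduce. They need 9 to be the SD, although the text calls it a variance. At 70 per arm, t-test power is 90% with no loss and 83% with 56 per arm (20% loss). At that ceiling, up to 28 of 140 primary values would be missing at month 12.

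**Assumed inputs, not in the documents.** Pre-operative mean 50-70 (SD 15), month 6 mean 82 (SD 11), month 12 mean 90 (SD 9). Correlations: pre-operative/month 6 0.3, pre-operative/month 12 0.3, month 6/month 12 0.6. Simulation: 70 per arm, normal scores, random loss, pass if the pooled-t 95% lower limit exceeds -5. Completers stand in for the PPS.

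**A. Month-6 carry, loss unrelated to outcome, true difference -5.** With a fraction f lost in each arm, the LOCF difference is (1 - f)(-5) + f × d6, where d6 is the month-6 difference. At f = 0.20 this is -4.0 for d6 = 0, -4.6 for d6 = -3 and -5.0 for d6 = -5.

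| Late loss | FAS alone, d6 = 0 / -3 / -5 | Both sets |
|---|---|---|
| 20% | 8.7 / 4.2 / 2.5% | 2.1 / 1.5 / 1.1% |
| 10% | 4.9 / 3.3 / 2.4% | 2.1 / 1.7 / 1.4% |
| 5% | 3.5 / 2.9 / 2.4% | 2.1 / 1.9 / 1.7% |

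At a true difference of 0 and late loss of 20 / 10 / 5%, power is 84 / 87 / 89% in the FAS and 83 / 87 / 89% in completers. Both sets pass in 77% at 20% loss.

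Unequal random loss has its own effect. In a separate illustration (SD 9, carried scores 10 points low, carried difference -5), 10% missing in the test arm and 20% in the control arm turn a true -5 into about -4.0. The FAS then passes falsely in 7.5% and both sets in 2.4%.

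**B. Month-6 carry, subjects who fail after month 6 leave.** The true -5 arises from failures, and 5% of non-failures are lost in each arm. Hand check, with 25% of test subjects failing by 20 points and 40% of these leaving:
- Leavers who failed: 0.25 × 0.40 = 10% of the arm, 7 of 70. LOCF gives each about 82 - (90 - 20) = 12 points too many, which shifts the difference by 0.10 × 12 = +1.2.
- Other losses are each scored 82 - 90 = -8. Test: 0.75 × 0.05 × (-8) = -0.3. Control: 0.05 × (-8) = -0.4. Net +0.1.
- LOCF difference: -5 + 1.2 + 0.1 = -3.7.
- Completers: failures make up 0.15/(0.15 + 0.7125) = 17.4% of the test arm, and 0.174 × (-20) = -3.5.

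For this pattern the false-pass rates are LOCF 11.1%, completers 13.5%, both 9.2%, and complete data 2.7%. Four failure patterns were tried (test/control 25%/0% and 30%/5% failing by 20 points; 12.5%/0% and 17.5%/5% failing by 40):

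| Failures who leave | FAS | Completers | Both |
|---|---|---|---|
| 20% | 5.8-7.5% | 4.9-6.9% | 4.1-5.9% |
| 40% | 10-15% | 11-15% | 8-13% |

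Complete data give 2.6-3.6%.

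**C. Pre-operative carry (less natural reading), loss unrelated to outcome.** With 10% early and 10% late loss and a true difference of 0, FAS power is 48-71% and both sets pass in 45-66%. Early loss of 12.5% test against 7.5% control shifts a true 0 by 0.05 × (20 to 40) = 1.0 to 2.0 points against the device. With the imbalance reversed and a true -5 (month-6 difference -3), the FAS falsely passes in 11-15% and both sets in 1.6-2.0%.

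**Remedy.** Multiple imputation (10 imputations, pre-operative mean 60, site not simulated), loss unrelated to outcome: both-sets power is 80-86% and the false-pass rate 1.6-2.2%. Under B with 40% of failures leaving (the two patterns with no control failures), imputation passes falsely in 14-15% with no shift, 3.7-8.0% after a 10-point shift and 0.7-3.5% after 20 points.

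**The case against.** The strongest reply has four parts.

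1. Using FAS and PPS is ordinarily read as requiring both. On that reading random loss is harmless: every both-sets figure under A is at or below about 2.1%. This stands, but the text does not state it, and one sentence would settle it.

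2. Endpoints are listed only at months 6, 12 and 24, so a pre-operative score is not the natural carried value; if it counted, the membership condition would exclude almost nobody. This stands too. C shows what the open wording permits, not what is likely.

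3. Replacing LOCF does not cure the worst case. Under B with 40% of failures leaving, the both-sets false-pass rate was 10.1% with LOCF against 12.7% with imputation in one pattern, and 12.3% against 14.3% in another. This is correct. Imputation is justified by visit timing and unequal random loss, and outcome-dependent loss needs its own remedy.

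4. The separate SAP may contain all of this. It may, so the point is limited to the supplied text.

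A reader might also infer that nothing planned would reveal outcome-dependent loss. The documents do not support that: 12.1.2 compares dropout and lists reasons, and adverse events and reoperation are followed throughout. These are descriptive; they could signal the problem but neither correct nor size it. Nor do the documents support the inference that LOCF always favours the investigational screw. The direction depends on the month-6 difference and on which arm loses more.

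**Conclusion.** The point holds for the supplied text and should be fixed. LOCF is the only method named, there is no missing-data sensitivity analysis, and the success rule does not say how the two sets combine.

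With month-6 carry and loss unrelated to outcome, the FAS-alone false-pass rate is 2.4-8.7% against a nominal 2.5%. The top of that range needs the full 20% loss to occur after month 6 and a 5-point deficit wholly absent at month 6. Requiring both sets brings it to about 2.1% or less. If failing subjects leave, both sets can pass falsely in about 4-13%, and requiring both does not restore 2.5%.

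The gap in the text is certain; the size of harm is not. Means, SDs other than 9, correlations, failure rates and leaving rates are all assumed.

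**What to change.** 1. **Sections 12.7 and 12.9.1.** Replace LOCF as the primary method with multiple imputation of the month-12 score from pre-operative and month-6 Lysholm, treatment and site, or an equivalent MMRM. Keep LOCF at most as a sensitivity analysis using month-6 scores only. This removes bias from visit timing and unequal random loss, but not from outcome-dependent loss.
2. **Outcome-dependent loss.** Pre-specify a tipping-point analysis that lowers imputed test-arm scores in steps until the lower limit reaches -5, and state before database lock the largest shift considered plausible. Report it as a sensitivity analysis, not a gate: at a true 0 with 10% random late loss, the pass rate would fall from 88% to 70% after a 10-point shift and 42% after 20. In 10.1.4.4, seek the 12-month Lysholm score after withdrawal where consent allows, using the remote scoring in schedule footnote 8.
3. **Section 12.5.** State that the lower limit must exceed -5 in both FAS and PPS.
4. **Section 12.9.1.** State that a pre-operative score may not stand as the 12-month result.

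The cost is wording, some extra analysis and some contact with withdrawn subjects, with no added patients or scheduled visits. Both-sets power is about 80-86% under random loss. At 20% late loss it is 80% with imputation, against 77% with LOCF. If the separate SAP already contains these items, the protocol only needs to match it.
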